#### Overview study plan.

Consecutive cervical cancer patients planned for robotic surgery, clinically stage 1A2 to 2A1.

Cervical injection of ICG and a total of 80 MBq Tc99 nanocolloid (the first 75 patients) and if the combination of nanocolloid and ICG after analysis better than ICG alone a continued combined use. If ICG or radiocolloid alone is equal or superior to the combined use in terms of technical success rates, the study will continue with the use of ICG or radiocolloid alone as tracer according to sample size analysis.

Registration of adverse events during insufflation and placement of port including necessary adhesiolysis.

Pelvic SLN identification with near infrared technique (and gamma probe first 75 patients) for identification of Indocyanine green (ICG) in lymphatics and lymph nodes. Ipsilateral cervical reinjection of ICG in case of non-display of any lymphatic pathway. Separate removal of the upper lymphovascular parametria. Registration of SLN- associated intraoperative adverse events.

Sentinel node in cervical cancer Version 1.2 180914 Frozen section of SLN and upper lymphovascular parametria.

A full pelvic lymphadenectomy after removal of SLN according to the Swedish National treatment protocol extended to the level of the inferior mesenteric artery in case of metastatic SLN's. Robotic Surgery with a Querleu Morrow B2 to C2 radical hysterectomy as appropriate or an aborted hysterectomy in case of metastatic SLN. Adnexal surgery as appropriate. Registration of associated intraoperative adverse events.

SLN's for ultrasectioning and immunohistochemistry. The remaining nodes for standard pathological bisectioning and staining with hematoxylin/eosine.

Registration of postoperative adverse events until 30 days after surgery using the Clavien Dindo classification.

Continuous data management. Analysis of technical success rates, sensitivity and false negative rates for SLN's comparing ICG with Radiocolloid after first 75 patients. In case of ICG + radiocolloid superior to ICG alone continued enrollment of patients using both tracers. In case of any of ICG or radiocolloid alone equal or superior to the combination continuation of the study for an interim analysis after 36 node positive patients (see section 11).

#### **1. OBJECTIVES**

To estimate ICG and Radiocolloid alone and in combination to estimate any advantage of the combination of both tracers in terms of technical success rates/ bilateral mapping, sensitivity and false negative rates for the detection of pelvic SLN (first 75 patients).

To estimate the sensitivity and negative predictive value of the pelvic sentinel lymph node (SLN) concept for determination of lymph node metastases in patients with early stage cervical cancer planned for robotic surgery using either a combination of ICG and Radiocolloid or in case ICG alone is equal to or superior (in terms of technical success rate, bilateral mapping rates) to the combination the use of ICG as tracer for cervical injection using an anatomically based surgical algorithm and definition of sentinel lymph nodes.

To estimate if reinjection of tracer (ICG) will enhance the technical success / bilateral mapping rates.

To estimate the proportion of cervical cancer patients suitable for the SLN concept in conjunction with robotic surgery

To estimate complications associated with the detection and removal of SLN as such.

To estimate complications associated with ICG as tracer.

To estimate the incidence of lymphatic complications by the use of a validated questionnaire

#### 2. BACKGROUND

The surgical approach for cervical cancer staging has changed from conventional laparotomy to a more minimally invasive technique with proven advantages in terms of less perioperative morbidity. Robotic assisted laparoscopic radical hysterectomy with pelvic lymph node dissection has emerged as the approach of choice for an increasing number gyne-oncologists worldwide. Previous data from the department of Obstetrics and Gynecology in Lund, Sweden, shows that robot assisted surgery feasible for 95% of unselected cervical cancer patients selected for primary surgery. In cervical cancer, nodal involvement is a strong prognostic factor and also determines

adjuvant treatment and a pelvic lymphadenecomy is recommended for cervical cancer stages 1a2 and higher stages where primary surgery is recommended. A pelvic lymphadenectomy is associated with an increased risk for lymphatic complications such as lymphedema, lymphocysts and in rare cases lymphatic ascites.

The concept of identifying nodal metastases by detection of sentinel lymph nodes as a marker of nodal metastatic disease or not therefore is appealing. However, during later years many studies have been published, most of the retrospective, using a variety of tracers and with little or no information on used surgical algorithm, used definition of SLN and without reference to lymphatic anatomy. Moreover, technical success rate varies. A high technical success rate is cruzial to avoid the need for a full hemipelvic or pathwaywize LND in case of failure. In pilot studies from Lund University we have shown that reinjection of tracer (ICG) increases the technical success rates both defined per hemipelvis and pathwaywize, defined by detection of at least one SLN per hemipelvis to around 95%. By the use of Indocyanine green, a fluorescent tracer, we have also previously demonstrated two bilateral separate pelvic pathways, the upper paracervical pathway (UPP) running along the upper lymphovascular parametrium usually to external iliac and/ or obturator nodes and the further lateral to the common iliac artery to paraaortic nodes and the lower paracervical pathway (LPP) running via the sacrouterine ligament to nodes medial of the internal iliac artery and/ or presacral nodes then further medial to the common iliac artery to paraaortic nodes. Hence there are two bilateral pelvic pathways draining further to the paraaortic region below as well as above the inferior mesenteric artery.

Surgical competence and experience is necessary to achieve a high technical success rate and a low false negative rate for SLN.

This study aims to evaluate the pelvic sentinel node concept based on a defined surgical algorithm and with a clear definition of SLN based on described uterine lymphatic anatomy. The study setting including only high volume surgeons at two of more tertiary high volume centers enables an evaluation of the true potential of the pelvic SLN concept in cervical cancer.

This study aims to include consecutive early stage (Stage 1a2 to 2a1) cancer patients fulfilling criteria to ensure the results is representative for the cervical cancer population. Planned surgery may be a radical hysterectomy or a radical trachelectomy including a full LND after removal of identified SLN's or an aborted procedure in favour of radiochemotherapy in case of metastatic SLN's.

#### **3. PATIENT ELIGIBILITY**

#### **Inclusion Criteria**

-Women of age 18 years and older at the time of informed consent.
-Women with a pathologically proven cervical carcinoma of any histologic subtype, clinically stage 1a2- 2a1 planned for primary surgery
-Absence of any exclusion criteria

#### **Exclusion Criteria**

-Non consenting patients

-Ongoing pregnancy

-Inability to understand written and/or oral study information

-Who performance status III or more

-Previous lower limb lymphedema

-Surgical contraindication to a laparoscopic approach or lymphadenectomy at surgeons discretion.

-Anesthesiologic contraindication to a laparoscopic approach at the anesthetist's discretion

- Locally advanced disease or intraabdominal/distant metastases at preoperative CT, MRI or ultrasonography

- Radiologically suspect pelvic nodal metastatic disease according to the RECIST criteria

 $(\geq 1 \text{ node with} \geq 16 \text{ mm short axis diameter})$ 

-Allergy to Iodine

-Patients with a known liver disease

-Patients with a significant bleeding disorder or mandatory antithrombotic treatment.

#### Before surgery patients will be allocated to:

**Primarily:** Removal of pelvic SLN's followed by a complete pelvic lympadenectomy with boundaries as described below. SLN and the separately removed upper paracervical tissue will be sent for frozen section and later for ultrasectioning and immunohistochemistry. A Querleu Morrow B2 to C2 radical hysterectomy or a robotic abdominal radical trachelectomy will be performed and at surgeons' discretion an abortion of those procedures in case of metastatic SLN's. Adnexal surgery / transpositioning of the adnexae will be performed at surgeons' discretion and patients wish.

#### Surgeon eligibility

All included surgeons outside the primary investigating center must have had a case observation at the primary investigating center followed by a an approved site visit by the principal investigating surgeon at their home center ensuring adherence to protocol. All included surgeons at the primary investigating center were approved by the principal investigating surgeon.

All included surgeons must have a previous experience of at least 100 robot-assisted procedures.

The departments of pathology were coordinated in terms of principles for ultrasectioning and immunohistochemistry of SLN and management on non-sentinel lymph nodes.

#### 4.0 STUDY MODALITIES

#### **Surgical Procedures**

Patients with stage 1a2- 2a1 cervical cancer planned for primary surgery with either a Querleu-Morrow B2- C2 radical hysterectomy or a robotic radical trachelectomy.
Injection of tracer (a total of 80 MBq Technetium nanocolloid and 2,5mg ICG solution / 2,5 mg/mL) will be injected submucosally into the cervix ad 2-4-8-and 10 O'clock respectively at onset of surgery (first 75 patients).

- Scanning of pelvic side walls after a minimum of 20 minutes after injection and a transperitoneal or retroperitoneal evaluation of ICG uptake per pathway (UPP and LPP bilaterally)

- Detection and removal of SLN will follow a strict protocol with a proximal- presacral dissection before the distal external iliac-obturator nodal compartment dissection and with careful opening of the presacral, paravesical and pararectal planes to avoid leaking of tracer. SLN will be defined as describe below.

- Identified SLN's and the upper paracervical tissue will be sent for frozen section and further for final ultrasectioning and immunohistochemistry as described below.

- A full pelvic nodal dissection will be performed after the removal of SLN's.

- The described procedures in this protocol will be performed with robot-assisted laparoscopy and with removal of SLN and non-SLN's before the radical hysterectomy/ trachelectomy.

#### **Drug Information:**

Indocyanine Green solution (ICG) 2.5mg/mL.

Description: ICG (Pulsion medical system, PICG0025SE, Feldkirchen Germany) is a sterile, lyophilized green powder containing 25 mg of Indocyanine green with no more than 5% sodium iodide.

The ICG solution is prepared immediately before surgery and intended for single patient use. For preparation, 10mL of sterile water is injected directly into the lyophilized ICG in its glass vial. Invert the vial multiple times to ensure thorough mixing. Draw up 0,25 mL in six 1 mL syringes from the vial with ICG solution (2,5mg/mL) for the cervical injection. A  $0.6x38mm 23Gx1 \frac{1}{2}$  needle. The content of four of the syringes are used for the initial

Sentinel node in cervical cancer Version 1.2 180914 injection and in case of non-display of any pathway one or two of the other are used for an ipsilateral re-injection. The ICG solution is stored at room temperature. The solution is active for 6 hours, and should be discarded after that period of time. Manufacturer: Pulsion medical system, Feldkirchen Germany Availability: ICG will be provided by the manufacturer to each site.

Adverse Effects if ICG: All adverse effects are allergic in nature and occur in <1% of patients. Anaphylactic or urticarial reactions have been reported in patients with or without a history of allergy to iodides. If such reactions occur, treatment with the appropriate agents (e.g. adrenalin, antihistamines, corticosteroids) should be initiated.

Contraindications: Known hypersensitivity to iodine containing compounds. Known liver failure. Radioactive iodine uptake studies should not be performed for at least 1 week following the use of ICG.

Please refer to the current ICG package insert for complete prescribing information

#### Injection of Indocyanine Green (ICG)

- The ICG is prepared by thorough mixing of 10mL of sterile water with the lyophilized ICG in its vial creating a 2.5mg/mL concentration. The lot number, expiration date and dose injected (mg) will be recorded.

- Six separate sterile 1mL syringes is prepared with 0.25 mL ICG solution (0.625 mg ICG)in each syringe is prepared.

- A 0.6x38 mm 23G needle is attached to each syringe for the injection. A separate back table is used for the syringes.

- The ICG injection will be performed immediately before placement of surgical port and docking the robot.

- Half the ICG volume in each syringe is injected submucosally and half the volume 3 cm into the cervical stroma at 2-4-8-and 10 O'clock respectively to a total dose of 2.5mg ICG and a total volume of 1 mL. Time for injection is recorded.

- After injection of dye, a fornix presenter without an intracervical device is placed

- A second ipsilateral injection of 0,25mL ICG is performed in case of non-display of

either of the upper (UPP) or lower (LPP) paracervical pathways after a minimum of 10 minutes observation time after ICG injection. The injection is done at 3 and 9 O'clock respectively, half the volume submucosally and half the volume 3 cm into the cervix. - Display of the separate lymphatic pathways (UPP, LPP and IPP will be recorded after the first and if performed after the second injection).

#### Technetium  Nanocolloid

The nanocolloid (GitPharma S.R.L. Saluggia Italy) will be prepared at the radionuclide unit at Skåne University Hospital, Lund, 1-2 hours before injection in four separate syringes each contacting 0,5mL and 20 MBq nanocolloid. The injection was performed the same was as described above and performed before the injection of ICG. A laparoscopic gammaprobe (Neo2000® laparoscopic probe, Neoprobe Corporation Dublin OHIO) will be used for detection of the SLN's defined by radiotracer.

#### **Sentinel Node Identification**

The bilateral technical success rate of SLN identification is important to determine if this technique can be transferred to clinical practice. Previous studies at our institution using Technetium  Nanocolloid as single tracer have shown a bilateral mapping rate of 65% in tumors smaller than 20 mm and in all size cervical cancer of 59%. Based on pilot studies at our institution on cervical and endometrial cancer with the use of ICG we expect that the bilateral pelvic SLN identification (defined as at least one SLN per hemipelvis) will be 90% or more: We intend to separately study if reinjection of ICG will enhance the bilateral detection rate. A lower bilateral detection rate will lead to the need of full lymphadenectomy in a higher proportion of patients.

A clear anatomically definition of what is a SLN and a strict surgical algorithm as described in this study is important.

Importantly, accreditation of surgeons will be performed as described and is likely important to achieve a similar success rate as in pilot studies.

**The sentinel nodes** are defined as the juxtauterine ICG positive / radiopositive node with an afferent ICG positive lymphatics in each of the UPP and LPP respectively on each pelvic side with the potential of parallel lymphatics in the UPP to the external and obturator areas . These SLN are defined as **SLN type 1.** 

In case of a ICG positive lymph vessel where no nodes are ICG positive in that pathway, the node where the ICG positive lymphatic channel ends is defined as **SLN ICG type 2**. The definitions based on ICG positive lymphatic channels were only attributed for nodes defined by ICG but does not exclude that nodes were also defined by radiopositivity. Nodes macroscopically suspect of metastatic disease will be defined as **SLN Macro** regardless of ICG uptake or radiopositivity but with information on ICG and radiopositivity.

Importantly, to secure accuracy, the positions and types of SLN will be marked on an anatomical chart, recorded on a list with anatomical locations and placed in pre-labeled jars with corresponding names and numbers. The SLN will be defined as **SLNICG**,

**SLNICG+Radio**, and **SLNRadio** and for SLN defined by ICG also as type 1 and 2. This list is used by the department of pathology for reporting the results to minimize the risk of errors in location of nodes and which nodes are SLN's, the types of SLN as of above and non-SLN's. A copy of the list is kept in the patients study file. Nodes defined as SLN will have red labels on the jars, other nodes will have black labels.

SLN's will be sent for frozen section and final histological evaluation including ultrasectioning and immunohistochemistry as described. SLN's will be sent for frozen section during surgery for intraoperative decisions on the extent of lymphadenectomy (paraaortic or not), transposition of ovaries and abortion of the hysterectomy in favour of radiochemotherapy..

[figure not shown]
Before final removal of SLN, the pelvic side walls will be scanned with the gamma-probe to get an overview of radiopositivity per hemipelvis including the presacral area. After opening of the avascular planes as of below a renewed scanning with the probe will be performed. Finally, in case no SLN radio have been identified per pathway, a final scan with the probe will be performed after removal of SLN's. The display of ICG in the respective pathways will be evaluated a minimum 10 minutes after the injection of ICG, first transperitoneally, and if not seen, after opening of the retroperitoneal avascular planes

starting with the presacral plane, then the paravesical and pararectal planes leaving the lymphatics intact with the aid of switching between white light and the ICG mode (Firefly mode). In case of a non-display of a pathway an ipsilateral injection of ICG as described will be performed. (the comparison of bilateral mapping rates between ICG and radiotracer will be performed before any second injection of ICG). Another 10 minutes will be alloved for awaiting distribution of ICG in the respective pathways. To minimize disturbance by leaking ICG or radiotracer identification and removal of SLN's starts cranially, presacrally (along the LPP) and continues at the pelvic side walls along the UPP. After removal of SLN's the upper lymphovascular parametrial tissue is removed separately (defined as the tissue along the uterine artery, medial to the obliterated umbilical artery and caudal of the supravesical artery) as it may contain lymph nodes that may not be separated from the green lymphovascular tissue and hence be the juxtauterine lymph node.

After removal of sentinel nodes a complete compartmentwize pelvic lymphadenectomy is performed followed by the hysterectomy as appropriate.

Anatomical boundaries of lymph node compartments in the female pelvis							
Lymph node compartment	Proximal limit	Lateral limit	Distal limit	Medial limit			
External iliac area	Bifurcation of external and internal iliac artery	Genitofemoral nerve	Cloquets lymph node	External iliac vein			
Obturator fossa	Internal iliac vein	Ileopsoac muscle	Os pubis, obturator nerve	Obliterated umbilical artery			
Common iliac	Aortic bifurcation	Genitofemoral nerve	Bifurcation of external and internal iliac artery	Common iliac artery			
Presacral	Aortic bifurcation	Common iliac artery	Lower promontory	Hypogastric nerve (as distinction between right and left)			
Lower paraaortic	Inferior mesenteric artery	Ureter	Aortic bifurcation				
Higher paraaortic	Left renal vein	Ureter	Inferior mesenteric artery				

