#### Sentinel node in cervical cancer Version 1.2 180914 5.0 TREATMENT PLAN

-Intraoperative cervical injection of Tc 99 nanocolloid and ICG (immediately before onset of surgery)

-Intraoperative lymphatic mapping and sentinel node identification with robotic NIR/fluorescence imager and gamma probe will be used for an initial transperitoneal, then retroperitoneal evaluation of display of ICG fluorescence/ radiopositivity. The retroperitoneal dissection with opening of the avascular planes saving the lymphatic vessels will start presacrally then further with the pelvic side walls. The upper lymphovascular parametria will be kept intact by a careful opening of the pararectal and paraveiscal spaces. -An ipsilateral reinjection of ICG will be performed in case of non-display of either of UPP or LPP. If the sentinel node cannot be identified in a particular pathway following a 15-20 minute search, the case should be described as a ICG-negative mapping event for that pathway. A initial scanning of the pelvic side walls and presacral area will be performed - A reinjection of ICG will be performed in case of non-display of the UPP and LPP bilaterally.

-The results of the lymphatic mapping will be marked on the anatomic plan and the specimens and labeling of those will be according to descriptions above.

-The complete SLN algorithm should be adhered to, i.e in case of a ICG negative mapping (for **SLN type 1 and 2, ICG defined**) and / or radio negative mapping any macroscopically metastase suspect nodes should be removed and defined as **SLN macro**. All patients will be subject for at least a full pelvic lymphadenectomy after removal of SLN.

-The upper lymphocascular parametrial tissue (the tissue medial of the obliterated umbilical artery, with the supravesical artery as distal/ventral border, the ureter as dorsal border and including tissue adjacent to the inner side of the broad ligament) will be removed and evaluated the same way as SLN's. This is to investigate the presence of lymph node in the upper parametria, theoretically the most juxtauterine nodes, hence the SLN.

-All SLN and the upper parametrial tissue will be subject for later ultrasectioning and IHC Histopathologic evaluation.

 In case of metastatic SLN the lymphadenectomy will be extended to the level of the inferior mesenteric artery and the hysterectomy aborted in favour of radiochemoptherapy. In case of a planned trachelectomy this will be transformed to

a radical hysterectomy.

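### In the first 75 patients the ICG-alone success rate may not be independent of the gamma reading, because neither the reading order nor a pre-probe ICG record is specified

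*Combined protocol and SAP*

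**What the plan says.** Section 1 sets the first objective: "To estimate ICG and Radiocolloid alone and in combination to estimate any advantage of the combination of both tracers". The Overview gives both tracers to the same patients ("Cervical injection of ICG and a total of 80 MBq Tc99 nanocolloid (the first 75 patients") and states the rule for continuing with one tracer: "If ICG or radiocolloid alone is equal or superior to the combined use in terms of technical success rates". The rule has no margin, test or error rate.

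The readings are described under Sentinel Node Identification in section 4.0:
- Gamma, first scan: "Before final removal of SLN, the pelvic side walls will be scanned with the gamma-probe to get an overview of radiopositivity per hemipelvis".
- Gamma, second scan: "After opening of the avascular planes as of below a renewed scanning with the probe will be performed".
- Gamma, third scan, conditional: "in case no SLN radio have been identified per pathway, a final scan with the probe will be performed after removal of SLN's".
- ICG: "The display of ICG in the respective pathways will be evaluated a minimum 10 minutes after the injection of ICG, first transperitoneally". If ICG is not seen, it is read again after the same planes are opened.

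Section 5.0 treats the two instruments as one mapping step: "sentinel node identification with robotic NIR/fluorescence imager and gamma probe will be used for an initial transperitoneal, then retroperitoneal evaluation".

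Some separation of the tracers is planned. ICG and radiotracer are compared before any ICG reinjection. ICG display per pathway is recorded after the first injection. Nodes are classed as ICG, ICG plus radio, or radio only, and specimen jars carry both tracer results.

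**The concern.** ICG success depends partly on where and how long the surgeon looks. Section 5.0 calls a pathway ICG-negative only after a search of 15 to 20 minutes. A hot spot found before or during that search can direct it, and a green node then found counts for ICG. If the study goes on with ICG alone, later patients have no such help. ICG-visible channels can equally steer the probe.

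What is at stake is the tracer decision after patient 75 and the reported ICG-alone and radiocolloid-alone rates. Every patient is planned for at least a full pelvic lymphadenectomy (section 5.0), so the issue is the validity of the comparison.

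**Working it through.** The number 75 has no stated derivation, so there is no plan figure to reproduce. The check has two parts.

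**1. Does the plan separate the two readings?**
- *Order.* The gamma scans and the ICG reading stand in one paragraph and are not ordered against each other. The second scan and the retroperitoneal ICG reading share a surgical stage. Pathways that need that stage are the difficult ones, and they decide the comparison.
- *Timing.* The minimum times do not settle the order. The ICG injection text and Sentinel Node Identification give 10 minutes. Surgical Procedures gives 20 minutes for side-wall scanning and ICG evaluation together. These times must be reconciled.
- *Masking.* No masking, second reader or pre-probe record is described.
- *Forms.* The display grid on the anatomic plan records ICG display by side and pathway, but has no gamma field and no sequence. Display is also not the endpoint, which is at least one sentinel node per hemipelvis. Jar labels give a node's tracer status. A node positive for both looks the same whichever tracer led to it.
- *Comparison before reinjection.* This removes the effect of a second ICG dose, not of the probe.

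**2. How large could the effect be?**

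Inputs from Sentinel Node Identification: expected bilateral ICG rate 90% (stated as 90% or more), and earlier bilateral radiocolloid rate 59% for all tumour sizes.

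Assumptions not in the documents: the two tracers fail independently; the combination succeeds when either tracer maps bilaterally; and a share g of radio-rescuable ICG failures is scored as ICG success because the probe steered the search.

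- Combination: 0.90 + 0.10 × 0.59 = 0.959.
- Gap to ICG: 0.10 × 0.59 = 5.9 points; 75 × 0.059 = 4.4 patients.
- Rise in apparent ICG rate: 5.9 × g points.
- The combination defined this way cannot fall below ICG, so equality needs zero radio-only patients. That has probability (1 − remaining gap)^75.

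| g | Patients moved | Apparent ICG rate | Remaining gap | Chance of observed equality |
|---|---|---|---|---|
| 0 | 0 | 90.0% | 5.9 points | 1.0% |
| 0.25 | 1.1 | 91.5% | 4.4 points | 3.4% |
| 0.50 | 2.2 | 92.95% | 2.95 points | 10.6% |
| 1 | 4.4 | 95.9% | 0 | 100% |

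If the true ICG rate were 80%, the gap would be 0.20 × 0.59 = 11.8 points. The same 25 to 50% would then move 2.95 to 5.9 points, or 2.2 to 4.4 patients.

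For scale, 68 of 75 has an exact 95% interval of 81.7 to 96.2%, and 44 of 75 has 46.7 to 69.9%. The shift is small beside 90% against 59%. It is not small beside the gap between ICG and the combination, which is a within-patient comparison and is what the rule turns on.

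The independence assumption can fail either way. Shared causes of failure would narrow the gap. Patients mapped on one side by each tracer would widen it.

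**The case against.** The strongest defence is that ICG success still requires fluorescence. A sentinel node defined by ICG needs a green node with a green afferent channel, or a green channel ending at a node. The probe cannot make an undisplayed pathway fluoresce, and a hot node with no ICG signal is classed as radio only. The search is systematic, with a set order of dissection and a set search time. This stands, and it limits the effect, but it does not remove it: a search can still be directed or prolonged by a hot spot.

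Four stronger readings are tempting, and the documents do not support them.
- A reader might infer that ICG is read with knowledge of the gamma result. The order is unspecified, and the transperitoneal ICG reading may come before any scan.
- A reader might infer that no ICG-alone rate exists. One can be tabulated from the planned records; what is unprotected is its independence.
- A reader might infer that the bias can only favour ICG. The third gamma scan has no ICG counterpart before reinjection. If its finds count, it adds radio-only successes and works against equality.
- A reader might apply 25 to 50% to all 75 × 0.10 = 7.5 expected ICG failures and get 2.5 to 5 points. The probe can help only where radiocolloid is detected, which leaves about 4.4 patients.

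Nor is an inflated rate carried into the later sample size. Sections 9 and 11 use an assumed 95% bilateral detection rate and proceed by the count of node-positive patients, and section 8 evaluates technical success on all injected patients who are not converted early. That a few patients can tip the decision also owes much to the missing margin, which is a separate matter.

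**Conclusion.** The point holds in a limited form. The two tracers are read in the same operation and at the same stage, with no masking, order or pre-probe ICG record specified, so the ICG-alone rate may not be independent of the gamma reading. On the protocol's 90% and 59%, with independent failures and an assumed 25 to 50% guidance share, the ICG rate would be raised by 1.5 to 2.95 points (about 1 to 2 of 75 patients) against a gap of 5.9 points. The guidance share has no source in the documents, and the third scan makes the net direction uncertain. This is more than missing detail, because the planned forms cannot show afterwards which tracer led to a node. It is a cheap improvement, not a fault that invalidates the study.

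**What to change.** In section 4.0 and on the anatomic plan form, for patients given both tracers:
- At each stage (transperitoneal, then after the planes are opened), log ICG display and ICG-defined sentinel nodes for every pathway before that stage's gamma scan. Keep all planned scans.
- Log any node or pathway found only after a scan as radiocolloid-added.
- Score ICG alone on the pre-probe entries and the combination on the final entries.
- Report radiocolloid with and without the third scan, and state which version enters the comparison.
- Show results by stage.

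The cost is a fixed recording order and one extra form column. There are two downsides. The radiocolloid rate must be described as ICG-assisted, so that part of the first objective is met only in weaker form. A hot spot on the transperitoneal scan could still influence the later retroperitoneal ICG reading, which is why results by stage are needed. For any patients already operated on without this record, the report should state that the order of reading is unknown.
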